5.3 Trial Design

This study is a single centre study in two stages with a STOP/GO checkpoint between stages. The first stage (STAGE 1) of the study will comprise a screening study for 18 months, in which 500 young men with stage 1 hypertension and no other evidence of cardiovascular disease will be stratified into two groups according to non-invasive measurement of their central aortic blood pressure (the LOW and HIGH CASP groups). The second stage of the study (STAGE 2) will comprise a 12 month RCT in the HIGH CASP cohort (treatment versus no treatment) utilising a Prospective Randomised Open Blinded Endpoint (PROBE) design ⁽⁵⁰⁾. The second stage of the study will also comprise a 12 month observational follow-up study of the LOW CASP cohort which will run in parallel with the RCT. The decision to proceed to STAGE 2 (STOP/GO checkpoint) will depend on whether the first part of our hypothesis is proven, i.e. that CASP will differentiate between those with and without cardiovascular structural damage (i.e. increased left ventricular mass index), measured using cMRI.

6. Methods

6.1 Site Selection

This is a single-site, investigator-designed and investigator-led study which will be performed within clinical research facilities available at University College London/University College Hospitals London NHS Trust.

6.1.1 Study Setting

Participants with stage 1 hypertension will be identified for recruitment from patients attending the blood pressure clinic at University College Hospital London or from local general practice surgeries in the north/central London community. All study procedures will be carried out in a research outpatient facility either at University College London Hospital (Clinical Research Facility, Elizabeth Garrett Anderson Wing, UCLH) or at University College London Institute for Cardiovascular Science (Clinical Research Facility, [name]). cMRI imaging will be carried out in the Institute of Cardiovascular Science British Heart Foundation funded Imaging Facility (Great Ormond Street Hospital, London).

6.1.2 Site/Investigator Eligibility Criteria

To participate in the TREAT CASP study, investigators and the trial site must fulfil a set of criteria that have been agreed by the TREAT CASP Trial Steering Committee and that are defined below. The trial site, will be issued with the applicable TREAT CASP documentation to use when applying for Site-Specific Approval (SSA).

6.1.2.1 Principal Investigator's (PI) Qualifications and Agreements

The investigator(s) must be willing to sign a UCL CTU Investigator Agreement to include compliance with the trial protocol (confirming their specific roles and responsibilities relating to the trial, and that the site is willing and able to comply with the requirements of the trial). This includes confirmation of appropriate qualifications, familiarity with the appropriate use of the drugs, agreement to comply with the principles of GCP, to permit monitoring and audit as necessary at the site, and to maintain documented evidence of all staff at the site where significant trial related duties have been delegated.

6.1.2.2 Resourcing at site

The investigator(s) should be able to demonstrate a potential for recruiting the required number of suitable subjects within the agreed recruitment period (i.e. the investigator(s) regularly treat(s) the target population). They should also have an adequate number of qualified staff and facilities available for the foreseen duration of the trial to enable them to conduct the trial properly and safely.

The trial site will be expected to complete a delegation of responsibilities log and provide staff contact details.

The site should have sufficient data management resources to allow prompt data return to UCL CTU.

6.2 Site approval and activation

On receipt of the signed Clinical Trial Agreement or Investigator Agreement, approved delegation of responsibilities log and staff contact details, written confirmation will be sent to the site PI. The trial manager or delegate will notify the PI in writing of the plans for site initiation.

The site must conduct the trial in compliance with the protocol as agreed by the Sponsor which was given favourable opinion by the Research Ethics Committee (REC) and/or Institutional Review Board (IRB). The PI or delegate must document and explain any deviation from the approved protocol, and communicate this to the trial team at UCL CTU.

6.3 Participants

6.3.1 Eligibility Criteria

This study will recruit young men with stage 1 hypertension, in accordance with the study hypothesis, aims and objectives.

6.3.1.1 Participant selection

There will be **NO EXCEPTIONS** (waivers) to eligibility requirements at the time of recruitment. Questions about eligibility criteria should be addressed PRIOR to attempting to recruit the participant.

The eligibility criteria for this trial have been carefully considered and are the standards used to ensure that only medically appropriate participants are entered. Participants not meeting the criteria should not be entered into the trial for their safety and to ensure that the trial results can be appropriately used to make future treatment decisions for other people with similar diseases or conditions. It is therefore vital that exceptions are not made to these eligibility criteria.

Participants will be considered eligible for enrolment in this study if they fulfil all the inclusion criteria and none of the exclusion criteria as defined below.

6.3.1.2 Participant Inclusion Criteria

- Men aged 18-54 years.
- A diagnosis of stage 1 hypertension using conventional brachial BP measurements confirming a seated blood pressure of 140-159/90-99mmHg and/or or a day-time average greater than or equal to 135mmHg on ambulatory blood pressure monitoring.
- No current treatment for hypertension (if previously treated with anti-hypertensive medication, patients will have received no treatment for > 3 months).
- Willing and capable of giving informed consent.

6.3.1.3 Participant Exclusion Criteria

- Women of any age.
- Stage 2 hypertension, i.e. brachial blood pressure ≥160/100mmHg.
- Secondary hypertension, e.g. renal artery stenosis, Conn's adenoma phaeochromoctytoma, aortic coarctation.
- Stage 1 hypertension with evidence of overt target organ damage on routine clinical testing (e.g. ECG LVH, renal impairment, proteinuria), and/or concurrent cardiovascular disease (e.g. stroke, TIA, cardiac or peripheral vascular disease) and/or diabetes mellitus i.e. risk factors

that would indicate that the stage 1 hypertension should be treated according to current guidance (NICE CG 127).

- Men in whom it is not possible to measure conventional brachial blood pressure.
- Atrial fibrillation or any other significant pulse rhythm irregularity in whom blood pressure measurement is difficult and unreliable.
- Regular consumption of more than 28 units of alcohol per week, or use of recreational drugs.
- Chronic inflammatory diseases requiring concomitant steroids and/or non-steroidal antiinflammatory drugs.
- Known severe hepatic impairment.
- Known previous hypersensitivity to drugs used.
- Concurrent malignancy.
- Unwillingness to undergo, or contraindication to, MRI scanning.
- Current or recent participation (last 6 weeks) in an interventional clinical trial.
- Co-enrolment in a CTIMP or study of a non-investigational medicinal product.
- Any clinical condition for which the investigator would consider the patient unsuitable for the trial.

6.3.1.4 Eligibility Criteria for Individuals Performing the Study

This trial will be carried out by nurses, physicians, scientists and technologists experienced in the management and treatment of hypertension, experienced in techniques of non-invasive blood pressure and with experience in performing and interpreting magnetic resonance imaging.

6.3.1.5 Co-enrolment Guidance

Co-enrolment in any CTIMP or any other study of a non-investigational medicinal product is an exclusion criterion. Patients will not be permitted to enrol into a CTIMP or another study of a non-investigational medicinal product until their participation in this trial has been completed and at least 6 weeks has lapsed since the last intervention. There is no prohibition on co-enrolment into observational studies.

6.3.1.6 Screening Procedures and Pre-randomisation Investigations

Written informed consent to enter and be randomised into the trial must be obtained from participants, person with legal responsibility after explanation of the aims, methods, benefits and potential hazards of the trial and **BEFORE** any trial-specific procedures are performed or any blood is taken for the trial. The only procedures that may be performed in advance of written informed consent being obtained are those that would be performed on all patients in the same situation as a usual standard of care.

The TREAT CASP study is in two stages and includes an initial stage 1 screening study into which all participants will be enrolled. There will be no pre-screening procedures prior to enrolment into the stage 1 screening study. Adherence to inclusion/exclusion criteria will be established from enquiring into potential participants' medical history. However, a seated measurement of brachial blood pressure may be performed during pre-screening as a part of normal clinical care.

6.3.1.7 Stage 1 Screening Study; Stratification of Participants by Central Aortic Systolic Pressure (CASP).

The first part of this study will identify ~500 men aged 18 – 54 years from the University College London Hospitals blood pressure out-patient clinic or from local General Practice surgeries, who have stage 1 hypertension based on seated conventional brachial BP measurements according to criteria set out by national NICE guidelines (BP 140-159/90-99mmHg and/or mean day-time blood pressure greater than or equal to 135/85 mmHg on ambulatory blood pressure monitoring). Potential participants will be given study specific information (participant information sheet) and will have had the opportunity to discuss potential participation in the study with a member of the research study team, prior to arranging an appointment to attend for a stage 1 screening study visit. At the stage 1 study visit we will outline what participation entails for the potential participant and answer any questions they have regarding participation in the study. We will then obtain and document informed consent to participate. Adherence to study inclusion and exclusion criteria will be ensured by questioning potential participants about their medical history, prior to enrolling the participant into the screening (stage 1) phase of the study and allocating a study specific identity. Stage 1 study participants will be recruited according to the study eligibility criteria as defined above and will have no evidence of existing target organ damage, cardiovascular disease, diabetes or chronic kidney disease. Once consented to participate in the TREAT CASP study, participants will undergo a cardiovascular health screen which will involve a number of routine clinical assessments, together with a study-specific non-invasive measurement of CASP.

Clinical assessments to be performed during the screening stage:

- Informed consent.
- Medical and lifestyle history.
- Physical examination.
- Seated Brachial BP and CASP using the CASPro device.
- Height and weight.
- Body fat composition using non-invasive bio-impedance.
- Blood tests: haematology, biochemistry, lipid profile and glucose (non-fasted), renal function (eGFR).
- Urinary albumin:creatinine ratio / urine dip stick for blood and protein.
- 12-lead ECG.
- 24hr brachial Ambulatory Blood Pressure Monitoring (Spacelabs device).

The ABPM measurement will be undertaken at screening to exclude participants with "white coat hypertension" as defined by the current NICE guidance ⁽⁴⁾. This requires a minimum of 14 daytime readings, 30 minutes apart (usually 08.00hrs-22.00hrs). The daytime average is then used to define

the participants' BP status. An ABPM daytime average of \geq 135/85mmHg excludes white coat hypertension. This ABPM diagnostic threshold is taken from the current NICE guidance on hypertension (NICE CG 127).

Data collected as part of the stage 1 screening study will primarily be used to stratify participants according to their central aortic systolic blood pressure and to identify those to be approached to participate further as participants in the subsequent randomised clinical trial and observational follow-up study. However, data from all stage 1 participants will also be used as cross-sectional data to investigate relationships between CASP and demographic or clinical parameters in patients with stage 1 hypertension. This will provide novel findings in patients with this condition. The Stage 1 screening phase will take up to 18 months to complete.

6.3.1.8 Defining the LOW CASP and HIGH CASP Groups - Stratification According CASP

After 500 participants have been recruited into the stage 1 screening study, data from participants will be stratified according to their CASP values. Based on the distribution of CASP values from our previous studies, we will select the upper 25% of CASP values to define the HIGH CASP group (n=130) who will be invited to participate in the RCT if the study progresses to the second stage. We will also select 65 participants with the lowest CASP values who will form the LOW CASP observational cohort and will be invited to participate in the observational follow-up study. Our preliminary data suggests that stratifying the stage 1 study population in this manner will result in an upper limit CASP value for the LOW CASP group of 129mmHg, and lower limit value for the HIGH CASP groups. We recognise that this will most likely generate two groups with different brachial BP values as well different CASP values. However, according to current guidance, treatment would not be offered on the basis of the brachial BP value alone. Furthermore, CASP cannot be predicted from the brachial BP and we are specifically evaluating the use of CASP to stratify the patients for treatment.

We plan to screen up to 500 participants in Stage 1 of the study, however, as screening proceeds, the distribution of CASP values will be monitored and modelled by the study statistician. It is possible that fewer people will need to be screened to identify the required number of participants for the LOW CASP and HIGH CASP cohorts with the desired CASP separation.

Once identified, people in the HIGH CASP (n=130) and the LOW (n=65) groups will be invited to return to the research unit to undergo cardiac MRI for detailed evaluation of left ventricular mass index (LVMI) and cardiac and vascular structure and function. This evaluation will dictate whether the TREAT CASP study progresses to the stage 2 randomised clinical trial and observational follow-up study.

6.3.1.9 STOP/GO Checkpoint:

A STOP/GO checkpoint has been incorporated into the study design which will be evaluated before the study proceeds to the second stage. The STOP/GO checkpoint will be implemented to avoid futility in implementing the second part of the study i.e. if there is no difference in cardiac structure between the HIGH and LOW CASP cohorts there would be little likely benefit in stratifying participants by their central BP for subsequent treatment for blood pressure lowering.

Cardiac MRI (cMRI) will be used to measure left ventricular mass index in participants from the HIGH and LOW CASP groups participating in the stage 1 screening study. This data will be used to evaluate

the STOP/GO checkpoint. If a difference in LVMI is observed between participants from the HIGH and LOW CASP groups, the null hypothesis that there is no difference in LVMI between groups will be rejected and the study can proceed to the second stage. If the null hypothesis is not rejected i.e. if there is no difference in LVMI between people from the HIGH and LOW CASP groups, the TREAT CASP study will be terminated at this point. This evaluation will be used to confirm or refute the first key element of our hypothesis, i.e. whether CASP has been effective at identifying patients with and without pressure-related target organ damage, irrespective of their brachial blood pressure values.

The decision to proceed to the second stage of the study will be taken by the Trial Steering Committee. The data upon which the STOP/GO decision is made will be reviewed by an independent statistician who will provide recommendations to the Trial Steering Committee.

6.3.1.10 STAGE 2 Randomised Clinical Trial and Observational Follow-up Study:

If the conditions of the STOP/GO checkpoint are met i.e. if stratification by CASP value identifies groups with differing pressure related cardiac damage (LVMI), the study will proceed to the second stage. The second stage of the TREAT CASP study incorporates a 12 month randomised controlled trial in the HIGH CASP group using a prospective, randomised, open label, blinded end-point (PROBE) design ⁽⁵⁰⁾. The RCT is designed to evaluate whether people from the HIGH CASP group benefit from BP lowering drugs compared to no treatment (usual care) with regard to regression of their baseline cardiovascular structural damage (elevated LVMI relative to the LOW CASP group). The degree of regression of cardiovascular structural damage (LVMI) between the intervention and the usual care groups constitutes the primary outcome for the TREAT CASP study and will be evaluated following completion of the RCT (after 12 months treatment) following a repeated cMRI evaluation.

The second stage of this study also incorporates an observational follow-up of the LOW CASP group (n=65) with repeat cMRI after 12 months. This is designed to evaluate whether there is any development or progression of cardiovascular structural changes if people with LOW CASP are left untreated for 12 months.

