5.1.1 Hypertension in the Young

For more than a century, the diagnosis of hypertension has been based on the measurement of brachial BP using an occluding cuff, inflated around the upper arm. However, the decision to treat BP is based not only on the patients' BP but also their risk of cardiovascular disease ⁽⁴⁾ as indicated by i) the presence of established cardiovascular disease; ii) the presence of pressure-mediated damage (e.g. left ventricular hypertrophy; markers of renal disease; the presence of hypertensive retinopathy) - so called "target organ damage", or iii) high cardiovascular risk (CV risk) based on formal estimation using CV risk calculators. Age is a major determinant of risk for CV events ⁽⁵⁾; consequently most research has focussed on assessing and treating older people, who are more likely to develop measurable clinical end-points within the typical duration of clinical trials, such as morbidity and mortality resulting from stroke and heart disease. As a result, most of the evidence base used to formulate national treatment guidelines has been acquired from people over 55 years of age and there is a paucity of research data upon which to base treatment decisions for younger people with hypertension ⁽⁶⁻⁸⁾. This has created a major dilemma for NICE in formulating its hypertension treatment guidelines – how and when to treat younger people with hypertension? This dilemma is recognised in the current NICE guidance on treating hypertension in Primary care (NICE CG 127, 2011) which identifies as a major research priority "the need to define the best methods to stratify younger people (i.e. aged \leq 40 years) with high blood pressure for treatment". In such younger people, if the brachial BP is $\geq 160/100$ mmHg (stage 2 hypertension), current guidelines recommend treatment ⁽⁴⁾. However, for the large number of younger people with stage 1 hypertension (brachial BP 140-159/90-99mmHg), there is uncertainty about the benefits of treatment unless the patient already has evidence of overt target organ damage, established cardiovascular disease, chronic kidney disease or diabetes. It is accepted that the use of formal 10 year CV risk calculations has little validity in these younger age groups and in any case, is unlikely to accurately reflect their lifetime risk. The issue of when to treat younger people with stage 1 hypertension is not insignificant. A recent study involving over 30 years of follow-up of over 1 million young male Swedish army recruits suggested that stage 1 hypertension in young people may not be benign and is associated with an increased risk of cardiovascular mortality ^(9,10). The question remains as to whether simple tools can be developed to better assess which younger people with stage 1 hypertension should be treated.

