
5.1.2 Inadequacies of Conventional Blood Pressure Measurement

The brachial BP (BrBP) method for measuring BP has changed little for more than a century, apart from the fact that automated oscillometric methods are progressively replacing manual auscultation. The assumption has always been that the pressure measured in the arm is

representative of the pressure throughout the circulatory system. However, it has long been recognised that pressure (particularly systolic and pulse pressure) is amplified as it moves from the aortic root to the peripheral circulation, i.e. the brachial artery ⁽¹¹⁾. If this relationship was fixed in all individuals, in all circumstances, throughout life, this amplification of pressure would not matter because the BrBP, if not an exact measurement of aortic root pressure, would always be proportional to the aortic root pressure. Unfortunately, this is not the case. We and others have shown that the amplification of brachial systolic blood pressure (BrSBP) can vary markedly and is profoundly influenced by age, gender, vascular disease (especially aortic arteriosclerosis and stiffening), heart rate and drug therapies used to treat hypertension (12-17). Importantly, we and others have shown that the variation in the relationship between central aortic systolic pressure (CASP) and BrSBP is particularly marked in younger people and paradoxically, those with the healthiest, most compliant arterial systems ^(13,18), [Appendix figure 1]. The difference between CASP and BrSBP whilst typically around 10mmHg in older people, i.e. aged >55yrs, can be as much as 30mmHg in younger people aged 18-40 years [Appendix figure 2]. This can give rise to the spurious diagnosis of hypertension in younger people, based on their brachial BP, and points to the fact that brachial BP measurements are not always the ideal way to categorise hypertension in younger people or to stratify their need for BP-lowering treatment. The inaccurate diagnosis of hypertension can have important implications for younger people, not only because of the anxiety and cost of treatment but also the impact of disease labelling on insurance weighting and some forms of employment. Therefore, it is particularly important to establish the correct diagnosis in younger people so as to avoid these consequences and exposure to life-long treatment that may not be necessary.

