6.5.2 Secondary Outcomes

Secondary outcomes in the TREAT CASP study are designed to evaluate mechanisms exploring the relationship between CASP vs. conventional brachial BP on extended markers of cardiac and vascular damage both in cross-sectional evaluations at the end of the STAGE 1 screening study and in longitudinal analysis during STAGE 2, after 12 months follow-up of the LOW CASP observational cohort and the HIGH CASP RCT.

Secondary outcomes for the TREAT CASP study will be:

- 1. LV mass/volume ratio;
- cMRI myocardial tissue tagging to demonstrate alterations in regional systolic and diastolic strain – early markers of hypertension-mediated damage;
- cMRI measurement of interstitial fibrosis using T1 mapping marker of damage as a prelude to impaired function;
- 4. cMRI measures of aortic distensibility and pulse wave velocity sensitive indices of aortic stiffening. This tests our subsidiary hypothesis that increased aortic stiffness causes the detrimental increase in CASP relative to brachial BP;
- 5. High resolution cMRI spin echo sequences to measure carotid and aortic wall thickness;
- 6. Albumin excretion rate (Urinary Albumin: Creatinine ratio) as an index of early renal injury;
- 7. Retinal photography to document hypertensive changes in retinal small vessels.

Detail regarding measurement of the secondary outcome variables is shown in section 6.10.1.

6.6 **Participant Timeline**

Participants in the TREAT CASP study will initially be recruited into the stage 1 screening study. Stage 1 screening study recruitment will remain on-going from study commencement (mid 2013) until 500 participants have been screened (~18 months). At this time, data from the stage 1 screening study will be collated and used to stratify participants into the upper and lower quartiles based upon their CASP values (HIGH and LOW CASP groups). Only those participants falling into the HIGH and LOW CASP groups will then be invited to return to the research centre to undergo cardiac MRI. Once participants in the HIGH and LOW CASP groups have undergone cMRI, the STOP/GO checkpoint will be evaluated (early 2015) to dictate whether the study proceeds to the second stage (stage 2 RCT and observational follow-up study). The study assessments in the stage 1 screening study have already been described (section 6.3.1.7) and are shown in the schedule of assessments below.

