Direct (aortic distensibility) and indirect (PWV) measurements of aortic stiffness will be undertaken in a single examination, utilising multiple sites along the aorta. Such measurements using MRI have previously been shown to exhibit good agreement compared to invasive measurements and show excellent reproducibility ⁽⁷⁶⁾. Stiffness can be determined at different levels of the aorta, which may be important for target organ damage and progression of disease. Possibly because the distance travelled between measurement sites in the aorta can be measured accurately by cMRI, differences in PWV can be detected between subjects with risk factors for CVD and healthy controls even with samples sizes less than 20 per group ⁽⁷⁷⁾. cMRI-measured aortic distensibility is an independent predictor of CVD morbidity and mortality in patients with chronic renal failure ⁽⁷⁸⁾. In the MESA study, reduced aortic distensibility in 800 middle aged and elderly subjects was related to age, hypertension, smoking and African-American ethnicity ⁽⁷⁹⁾. Additionally, reductions in diastolic function have been shown to be related independently to arterial stiffness for both aortic and carotid arteries ⁽⁸⁰⁾, and LV hypertrophy in patients free of clinical CVD.

6.10.1.9 Measurement of Carotid and Aortic wall thickness:

High resolution spin echo sequences will allow assessment of carotid and aortic wall thickness ⁽⁷⁷⁾. Although arterial wall thickness and stiffness both increase with age, there are important differences in associated risk factors for the two measures ⁽⁷⁹⁾ and increased stiffness can be demonstrated without any evidence of subclinical atherosclerosis on imaging ⁽⁸¹⁾. These findings emphasise the fact that, although related, arterial stiffness and wall thickening are not governed by the same underlying pathophysiological processes, which may explain why arterial stiffness is an independent risk factor for CVD.

6.10.1.10 Measurement of Myocardial Perfusion Reserve:

This is an indicator of combined macro- and microvascular coronary function which can be determined with absolute quantification of blood flow. Perfusion reserve was related to age and traditional risk factors, and reductions in strain, in the MESA study ⁽⁸²⁾ but the relationship to arterial stiffness and diffuse fibrosis in hypertension has not been studied to date.

6.10.1.11 Other Markers of Target Organ Damage;

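### Ranking men aged 18-54 on raw CASP will make the HIGH group older than the LOW group, yet the HIGH-LOW LVMI test is unadjusted and is read as evidence that CASP identifies pressure-related damage

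*Protocol*

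**What the plan says.** - **Who is ranked.** Section 6.3.1.2 admits "Men aged 18-54 years", most of them with seated brachial systolic pressure of 140-159 mmHg (an ambulatory route is also allowed).
- **How the groups are cut.** Section 6.3.1.8: "we will select the upper 25% of CASP values to define the HIGH CASP group (n=130"), and the 65 men with the lowest values form LOW. The section accepts that brachial pressure will differ between the groups. It does not mention age.
- **What CASP depends on.** Section 5.1.2 says that brachial amplification "can vary markedly and is profoundly influenced by age, gender, vascular disease". The gap is "typically around 10mmHg in older people, i.e. aged >55yrs", but "can be as much as 30mmHg in younger people aged 18-40 years".
- **The test.** Section 6.10.4.2.3 makes a significant HIGH-LOW difference in LVMI at P<0.05, by Student t-test, the condition for Stage 2. No covariate is named.
- **The reading.** Section 6.3.1.9 takes the result as confirming or refuting that CASP separates men with and without pressure-related organ damage. The hypotheses in 5.2.2 and questions 2 and 3 in 5.2.3 use the same contrast, and 6.4.8 makes LOW the reference level for regression in treated HIGH men.
- **Where age is adjusted for.** Section 6.10.4.2 lists age among potential confounders, but for the Stage 2 model of change in LVMI.
- **Age and the vascular outcomes.** Section 6.10.1.9: "Although arterial wall thickness and stiffness both increase with age". Section 6.5.2 includes the vascular measures "in cross-sectional evaluations at the end of the STAGE 1 screening study".

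**The concern.** CASP equals brachial systolic pressure minus the brachial-central gap. If the gap shrinks with age and brachial pressure is held in a band about 20 mmHg wide, a high CASP tends to mark an older man and a low CASP a younger one. HIGH and LOW then differ in age by construction.

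The adjustment sits in the wrong place. Age is a named covariate in the randomised comparison, where randomisation already balances it in expectation. It is absent from the non-randomised HIGH-LOW comparison, where nothing balances it.

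Two things are at stake. The STOP/GO result could be moved by age in either direction. And a statement that CASP itself identifies damaged hearts, or that treatment returns HIGH men to the LOW level, could partly be a comparison of older with younger men.

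**Working it through.** **1. The plan's own figure.** Section 6.7.2 gives 31 per group for a 10 g/m² difference, SD 11.8, 90% power, P=0.05 (two-sided assumed). n = 2 × [11.8 × (1.960 + 1.282) / 10]² = 29.3, so 30 by the normal formula. The t-based calculation gives 30.25, so 31. The figure reproduces.

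**2. What the checkpoint will detect.** With 65 LOW and 130 HIGH:
- SE = 11.8 × √(1/65 + 1/130) = 1.79 g/m².
- Smallest significant observed difference = 1.96 × 1.79 = 3.5 g/m². With an SD 50% larger (17.7) it is 5.3 g/m².

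The test is sensitive to differences well below the 10 g/m² that it was sized for, whatever their cause.

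**3. Age difference created by the selection.** The documents give no mean gap by age: the 30 mmHg is a maximum, and the 10 mmHg is for people older than those enrolled. So I assumed a range. CASP = brachial SBP − [10 + S × (54 − age)/36 + error], with brachial SBP uniform on 140-160, S the extra mean gap at age 18 compared with age 54, and error SD 4, 6 or 8 mmHg. From 500 men, take the 65 lowest and 130 highest. The ranges below run over the three SDs.

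| S (mmHg) | HIGH − LOW mean age, ages uniform 18-54 | HIGH − LOW mean age, ages weighted older |
|---|---|---|
| 0 | 0 years | 0 years |
| 3 | 2.7-4.2 | 1.3-2.0 |
| 5 | 4.5-6.7 | 2.3-3.3 |
| 10 | 9.0-12.4 | 4.5-6.4 |
| 15 | 12.7-16.8 | 6.6-9.3 |

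HIGH is older in every scenario with S above 0. Section 6.3.1.8 offers one anchor, an expected upper limit of 129 mmHg for LOW. The uniform-age scenarios at S = 15 put that limit at 120-123 mmHg, so I give them little weight. Scenarios within 2 mmHg of 129 give 1.3 to 6.7 years. The anchor is soft, because it moves with the assumed 10 mmHg gap at age 54. I therefore take one or two years to about 12 as the plausible range.

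**4. Effect on STOP/GO if CASP had no effect of its own.** The protocol gives no LVMI-age slope, so the true age-driven difference d is also assumed. Chance of P<0.05 by the two-sided t-test with 193 df and SE 1.79:

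| d (g/m²) | Example that produces d | Chance of a significant result |
|---|---|---|
| 0 | no age effect | 5% |
| 1 | 10 years × 0.1 per year | 9% |
| 2 | 10 years × 0.2 per year | 20% |
| 3 | 10 years × 0.3, or 6 years × 0.5 | 38% |

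If LVMI falls with age over this range, d has the opposite sign. It then works against a real CASP difference and could contribute to a wrong STOP.

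**The case against.** - **CASP is being tested as a stratifier, and a stratifier may work partly because it carries age.** This stands for the decision rule: it is a fair reason not to replace the t-test. It does not cover the wording in 5.2.2 and 6.3.1.9, which attributes the difference to pressure.
- **The other cross-sectional analyses may be adjusted in a statistical analysis plan that is not shown.** This stands. A reader might infer that every HIGH-LOW comparison is fixed as unadjusted, but only the STOP/GO LVMI test is. For wall thickness, distensibility and pulse wave velocity the protocol states no model either way.
- **The outcomes that the protocol ties to age are vascular, while the fixed unadjusted test is on LVMI.** This stands as a limit. Section 6.10.4.2 names age as a potential confounder of LVMI but gives neither sign nor size, so no direction of bias can be claimed.
- **The age difference is uncalibrated.** This stands for its size. A reader might take 16 years or more from the steepest assumptions, but those scenarios sit poorly with the 129 mmHg limit.
- **Question 2 rests partly on change within LOW men over a year.** This is correct, and that change is not a HIGH-LOW contrast.

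Two stronger readings are not supported. The primary outcome is not confounded, because it is a randomised comparison within HIGH. Nor does the age shift show that the trial misses its target population. Section 5.1.1 quotes a research priority, "the need to define the best methods to stratify younger people", there meaning age 40 or below, but section 5.2 openly defines younger as 18-54 for practical reasons, and section 6.10.4.2.5 plans no subgroups.

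**Conclusion.** The point holds for the HIGH-LOW contrast. By the protocol's own premise the HIGH group will be older, and the one HIGH-LOW test that the protocol fixes ignores age while its result is given a causal reading. The direction of the age shift follows from the text. Its size (one or two years to about 12) rests on assumed gap slopes, spreads and age distributions. The chance of a GO without any CASP effect, about 20-38% against a nominal 5%, rests on a further assumption of a 2-3 g/m² age-driven difference. Because the sign of age on LVMI is unknown, a masked real difference is equally possible.

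The consequence is limited to the interpretation of STOP/GO, the use of LOW as a reference level, and cross-sectional HIGH-LOW comparisons of age-related outcomes. It is worth correcting because the correction is cheap.

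**What to change.** - **Section 6.10.4.2.3.** Keep the t-test as the checkpoint rule. Add a pre-specified linear regression of baseline LVMI on group (HIGH or LOW) with age as a continuous covariate, reported as an estimate with its 95% CI.
- **Section 6.3.1.9.** Give that estimate, with the age distribution by group, to the independent statistician and the Trial Steering Committee together with the t-test.
- **Sections 5.2.2, 5.2.3 and 6.3.1.9.** State that any claim that CASP itself identifies damage will rest on the age-adjusted estimate.
- **Sections 6.4.8 and 6.5.2.** Use the same adjustment when LOW is the reference for treated HIGH men, and for HIGH-LOW comparisons of wall thickness, distensibility and pulse wave velocity.

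The cost is wording and one extra model, since age is known for every man. The adjusted estimate will be less precise because age and CASP overlap. The checkpoint can afford this: power for 10 g/m² with 65 v 130 men is above 99.9%, and about 96% if the SD is 50% larger.
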